- r. At each visit the participant will be asked if they have had a private/off-study COVID-19 test. If a participant receives a positive SARS-CoV-2 result from a private/off-study test (whether through PCR or serological testing) during the study, and the positive result occurs within 28 days after vaccination, the event will be reported as an AE. If it occurs after 28 days, the event will be recorded as an SAE only if the event qualifies as serious. If the event occurs after 28 days, and it is not serious, it will be reported in the eCRF. The participant can continue in the study for safety follow-up if they choose to; however, this must be in accordance

with local country and site level recommendations for COVID-19 and they will not be permitted to receive further study vaccination administrations. (see Section 8.3.1).

- s. MAAEs are to be reported for all participants from the moment of the 1st vaccination until 6 months after the last vaccination, except for MAAEs leading to study discontinuation which are to be reported during the entire study. New onset of chronic diseases will be collected as part of the MAAEs.
- t. Concomitant therapies such as analgesic/antipyretic medications and non-steroidal anti-inflammatory drugs, corticosteroids, antihistamines, and vaccinations must be recorded from the first dose of study vaccine until 28 days after administration of study vaccine, and thereafter, pre-dose on the day of subsequent vaccination and for 28 days after the subsequent dose of study vaccine. Refer to Section 6.8 for collection and recording of concomitant therapies associated with SAEs, solicited and unsolicited AEs, suspected AESIs, and MAAEs. All other concomitant therapies should also be recorded if administered in conjunction with new or worsening AEs reported per protocol requirements outlined in Section 8.3.1.
- u. At Visit 2, in addition to the diary, a ruler and thermometer will be distributed to each participant. At Visit 4, the site is to report the 2nd vaccination date in the eCOA portal to ensure that the appropriate diary is visible in the electronic diary.
- v. If an event is still ongoing on Day 8 or Day 64, the participant should continue to collect the information until resolution.

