- p. AEs and special reporting situations that are related to study procedures or that are related to non-investigational sponsor products will be reported from the time a signed and dated ICF is obtained until the end of the study/early withdrawal. All other unsolicited AEs and special reporting situations will be reported for each vaccination from the time of vaccination until 28 days post vaccination.
- q. All SAEs related to study procedures or non-investigational sponsor products will be reported for all participants from the time a signed and dated ICF is obtained until the end of the study/early withdrawal. All other SAEs are to be reported for all participants from the moment of first vaccination until completion of the participant's last study-related procedure. Suspected AESIs are to be reported from the moment of vaccination until completion of the participant's last study-related procedure (see Section 8.3.1).
- r. At each visit the participant will be asked if they have had a private/off-study COVID-19 test. If a participant receives a positive SARS-CoV-2 result from a private/off-study test (whether through PCR or serological testing) during the study, and the positive result occurs within 28 days after vaccination, the event will be reported as an AE. If it occurs after 28 days, the event will be recorded as an SAE only if the event qualifies as serious. If the event occurs after 28 days, and it is not serious, it will be reported in the eCRF. The participant can continue in the study for safety follow-up if they choose to; however, this must be in accordance with local country and site level recommendations for COVID-19 and they will not be permitted to receive further study vaccination administrations. (see Section 8.3.1).
- s. MAAEs are to be reported for all participants from the moment of the 1st vaccination until 6 months after the last vaccination, except for MAAEs leading to study discontinuation which are to be reported during the entire study. New onset of chronic diseases will be collected as part of the MAAEs.

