If a participant is unable to complete the study (post vaccination 1), but has not withdrawn consent, an early exit visit will be conducted, or the participant can continue with other study procedures. The end of study is considered as the last visit for the last participant in the study.

Study Procedures

For each group, safety will be assessed by collection of solicited local (at injection site) and systemic AEs, unsolicited AEs, MAAEs, AESIs, and SAEs. Other safety assessments include vital

signs measurements (heart rate, supine systolic and diastolic blood pressure, respiratory rate, and body temperature) and physical examinations at the time points indicated in Section 1.4.

After each vaccination, participants will remain under observation at the study site for at least 15 minutes for presence of any acute reactions and solicited events. Any solicited local or systemic AEs, unsolicited AEs, MAAEs, AESIs, SAEs, concomitant medications, and vital signs will be documented by study-site personnel following this observation period. In addition, participants will record solicited signs and symptoms in a diary for 7 days post vaccination.

The reporting periods of AEs, MAAEs, AESIs, and SAEs, and special reporting situations are detailed in Section 8.3. Reporting periods for concomitant therapy are outlined in Section 6.8. At each visit the participant will be asked if they have had a private/off-study COVID-19 test. If a participant receives a positive SARS-CoV-2 result from a private/off-study test (whether through PCR or serological testing)

- the participant can continue in the study for safety follow-up if they choose to:
 - This should be in accordance with local country and site level recommendations, including requirements for quarantine
 - They will not be permitted to receive further study vaccination administrations
 - The study staff will recommend the participant informs their medical care provider.
 - If there are no local country recommendations for COVID-19, the sponsor recommends the participant self-quarantines and does not come for a clinic visit until 2 consecutive negative PCR tests could be obtained.

In case the participant experiences signs or symptoms of COVID-19 after obtaining a positive SARS-CoV-2 test result, they should contact the study site at the time of symptom onset for recommendations on actions to follow for further care per local guidance.

See Section 8.3.1 on the reporting periods of this event.

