7. DISCONTINUATION OF STUDY VACCINATION AND PARTICIPANT DISCONTINUATION/WITHDRAWAL

7.1. Discontinuation of Study Vaccination

Study vaccinations will be withheld for the reasons listed below. These participants must not receive any further doses of study vaccine but should remain on study for follow-up with assessments of safety and immunogenicity as indicated in Section [1.4.1](#) and Section [1.4.2](#) (for the sub study), Schedule of Activities. Additional unscheduled visits may be performed for safety/reactogenicity reasons, if needed. In case of questions, the investigator is encouraged to contact the sponsor.

- Any related AE, worsening of health status or intercurrent illnesses that, in the opinion of the investigator, requires discontinuation from study vaccine
- The participant becomes pregnant
- Unblinding on the participant level that, in the opinion of the sponsor, would compromise the integrity of the data

^a Note: Ocular, topical or inhaled steroids are allowed.

- Unblinding of a study participant in order to receive an authorized/licensed COVID-19 vaccine
- Anaphylactic reaction following vaccination, not attributable to causes other than vaccination
- SAE or other potentially life-threatening (Grade 4) event that is determined to be related to study vaccine
- Chronic or recurrent use of systemic corticosteroids at immunosuppressive dose, and administration of antineoplastic and immunomodulating agents or radiotherapy
- Withdrawal of consent to receive further study vaccination
- Participant has a positive test result for SARS-CoV-2 infection during the study after screening and enrollment (see Section 8.3.1).
- Participant receives any experimental medication (including experimental vaccines other than the study vaccine) or receives an anti-COVID-19 vaccine or treatment
- Participant previously experienced TTS, including CVST or HITT or GBS.
- Participant experiences capillary leak syndrome after the first dose.

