At each visit the participant will be asked if they have had a private/off-study COVID-19 test. If a participant receives a positive SARS-CoV-2 result from a private/off-study test (whether through PCR or serological testing), the participant should contact the study site at the time the positive SARS-CoV-2 test result is obtained. The participant can continue in the study for safety follow-up if they choose to; however, this must be in accordance with local country and site level recommendations for COVID-19, including requirements for quarantine. These participants will not be permitted to receive further study vaccination administrations. The study staff will recommend the participant informs their medical care provider. If there are no local country recommendations for COVID-19, the sponsor recommends the participant self-quarantines and does not come for a clinic visit until 2 consecutive negative PCR tests could be obtained. If the participant experiences signs or symptoms of COVID-19 after obtaining a positive SARS-CoV-2 test result, they should contact the study site at the time of symptom onset for recommendations on actions to follow for further care. See section 8.3.1 on the reporting periods of this event.

Visit Windows

Visit windows are provided in Section 1.4, Schedules of Activities. The participant should be encouraged to come on the exact day planned and use the visit window only if absolutely necessary.

The timings of the post vaccination visits will be determined relative to the actual day of the corresponding vaccination.

If a vaccination window is missed due to a study pause (see Section 6.9), efforts will be made to still vaccinate the participant as soon as possible, even if out of window. The timings of the post vaccination visits will be determined relative to the actual day of the vaccination, unless they overlap with other scheduled visits, in which case the sponsor should be contacted to discuss optimal scheduling for these visits. If the participant does not want to receive the second vaccination, they can still continue with other study procedures.

Screening

Screening will be performed within 28 days prior to the first study vaccination or on the day of vaccination. If screening is performed on the day of vaccination, Visit 1 and Visit 2 will coincide

on Day 1. Screening must be completed and all eligibility criteria must be fulfilled prior to randomization and vaccination.

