Clinically relevant medical events not meeting the above criteria and occurring between signing of the ICF and moment of first vaccination will be collected on the Medical History eCRF page as pre-existing conditions.

Solicited AEs, collected through a diary, will be recorded for each vaccination from the time of vaccination until 7 days post vaccination.

All other unsolicited AEs and special reporting situations, whether serious or non-serious, will be reported for each vaccination from the time of vaccination until 28 days post vaccination. Unsolicited AEs with the onset date outside the timeframe defined above (>28 days after previous study vaccination), which are ongoing on the day of the subsequent vaccination, should be recorded as such.

At each visit the participant will be asked if they have had a private/off-study COVID-19 test. If a participant receives a positive SARS-CoV-2 result from a private/off-study test (whether through PCR or serological testing; for participants seropositive at baseline, only PCR testing applies) during the study, and the positive result occurs within 28 days after vaccination, the event will be reported as an AE. If it occurs after 28 days, the event will be recorded as an SAE only if the event qualifies as serious. If the event occurs after 28 days, and it is not serious, it will be reported in the eCRF. The participant can continue in the study for safety follow-up if they choose to; however, this must be in accordance with local country and site level recommendations for COVID-19 and they will not be permitted to receive further study vaccination administrations. Any positive SARS-CoV-2 result should be recorded in the eCRF.

All SAEs and AEs leading to discontinuation from the study/vaccination (regardless of the causal relationship) will be reported for all participants from the moment of first vaccination until completion of the participant's last study-related procedure, which may include contact for safety follow-up. The sponsor will evaluate any safety information that is spontaneously reported by an investigator beyond the time frame specified in the protocol.

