*Medical and scientific judgment should be exercised in deciding whether expedited reporting is also appropriate in other situations, such as important medical events that may not be immediately life-threatening or result in death or hospitalization but may jeopardize the participant or may require intervention to prevent one of the other outcomes listed in the definition above. These should usually be considered serious.

If a serious and unexpected AE occurs for which there is evidence suggesting a causal relationship between the study vaccine and the event (eg, death from anaphylaxis), the event must be reported as a SUSAR even if it is a component of the study endpoint (eg, all-cause mortality).

At each visit the participant will be asked if they have had a private/off-study COVID-19 test. If a participant receives a positive SARS-CoV-2 result from a private/off-study test (whether through PCR or serological testing) during the study, and the positive result occurs within 28 days after vaccination, the event will be reported as an AE. If it occurs after 28 days, the event will be recorded as an SAE only if the event qualifies as serious. The participant can continue in the study for safety follow-up if they choose to; however, this must be in accordance with local country and site level recommendations for COVID-19, and they will not be permitted to receive further study vaccination administrations. Any positive SARS-CoV-2 result should be recorded in the eCRF.

Unlisted (Unexpected) Adverse Event/Reference Safety Information

An AE is considered unlisted if the nature or severity is not consistent with the applicable product reference safety information. For Ad26.COV2.S, the expectedness of an AE will be determined by whether or not it is listed in the IB.

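### In baseline-seronegative participants, any positive off-study serology result bars dose 2, including spike tests that the protocol says the vaccine itself can turn positive

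*Protocol*

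**What the plan says.** Footnote r in Sections 1.4.1 and 1.4.2 has sites ask about off-study testing at every visit. It covers the case "If a participant receives a positive SARS-CoV-2 result from a private/off-study test (whether through PCR or serological testing) during the study" and states that "they will not be permitted to receive further study vaccination administrations". Section 4.1 (Study Procedures), Section 8 and Section 10.4.1 repeat the bar; Section 8 words it as "These participants will not be permitted to receive further study vaccination administrations".

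Section 8.3.1, to which the footnote refers, contains the only exception: "for participants seropositive at baseline, only PCR testing applies". The serology trigger therefore applies to participants seronegative at baseline, which means the whole main study by eligibility and the seronegative part of the sub study.

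Section 7.1 lists among the reasons for withholding vaccination: "Participant has a positive test result for SARS-CoV-2 infection during the study after screening and enrollment (see Section 8.3.1". It also says: "In case of questions, the investigator is encouraged to contact the sponsor".

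Footnote a to the humoral assay table (Synopsis, and Table 6 in Section 8.1) warns that vaccination can interfere with some tests run by community clinics or commercial laboratories. Such tests look for spike and may read falsely positive. Participants are therefore encouraged not to have serology done outside the study.

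The SAP counts an infection during the study only on a positive PCR/molecular test or on conversion in a non-spike assay (SAP 4.1, 5.1.5 footnote c, 6.1.4). Samples taken after a missed vaccination leave the PPI (SAP 4.1, 5.1.3).

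**The concern.** Spike antibody is the response that the vaccine is meant to produce. In someone who has had dose 1, a positive spike test is what a working vaccine would give, so it says little about new infection. The protocol recognises the hazard in the assay footnote, but the dosing rule takes no account of it.

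The participant at risk is an uninfected, baseline-seronegative responder who has an off-study spike test between Day 1 and Day 57 and reports the result when asked. As written, the rule withholds dose 2. The Day 71 sample then leaves the PPI, and with it the NI set, which is drawn from the PPI. Both analysis scenarios in SAP 4.2 are affected, since Scenario 2 uses the PPI directly. The Day 29 sample is not lost on this ground, so the one-dose comparisons and the Day 29 count that chooses between the scenarios are untouched.

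The participant also forgoes a scheduled dose for a reason that the protocol itself describes as possibly false.

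**Working it through.** **Step 1: the rule set against the warning.**

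| Place | Which off-study serology counts? | Exception |
|---|---|---|
| Footnote r (1.4.1, 1.4.2), 4.1, 8, 10.4.1 | Any | None |
| 8.3.1 | Any | Baseline-seropositive: PCR only |
| 7.1 | Refers to 8.3.1 | None written; sponsor contact if questions arise |
| Assay-table footnote a | Some spike tests may be falsely positive | Encouragement not to test |
| SAP infection definition | Non-spike conversion only | – |

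No passage limits the trigger by assay target or asks for confirmation. The encouragement lowers the number of such results. It does not say what to do with one that is reported.

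**Step 2: the plan's sample size.** Inputs from protocol Section 9.2: SD 0.5 (log10), margin log10(1.5) = 0.1761, true ratio 1, one-sided alpha 0.0125, power 90%, dropout 10.2%.

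n per arm = 2 × 0.5² × (2.2414 + 1.2816)² / 0.1761² = 200.1, so 201. Then 201 / 0.898 = 223.8, so 224, against 225 stated. With the t distribution n is 202, and 202 / 0.898 = 224.9, so 225. The plan's figure reproduces.

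**Step 3: how many could be affected.** The documents give no rate. I assume 1% to 5% of baseline-seronegative participants.

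- Target enrolment: 6 × 225 + 4 × 40 = 1,510, giving 15 to 76 participants.
- With protocol Table 7's arm sizes: 6 × 212 + 4 × 40 = 1,432, giving 14 to 72.

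These are enrolled participants. SAP Section 3 reports 38% N-positive at Day 71 in the main study. If that share is lost anyway and is unrelated to off-study testing, about 0.62 × 15 = 9 to 0.62 × 76 = 47 otherwise evaluable samples would go. Overlap between testing and true infection would lower this further.

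**Step 4: effect on power.** Two-sample t-test power (noncentral t) with the Step 2 inputs, both arms reduced by the same fraction:

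| Arms before the extra loss | No extra loss | 1% | 5% |
|---|---|---|---|
| 225 × 0.898 = 202 per arm | 90.1% | 89.8% | 88.4% |
| 265 vs 265, × 0.62 | 82.6% | 82.2% | 80.4% |
| 225 vs 265, × 0.62 | 79.0% | 78.5% | 76.6% |
| 252 vs 252, × 0.62 | 80.5% | 80.0% | 78.2% |
| 212 vs 252, × 0.62 | 76.5% | 76.0% | 74.1% |

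The × 0.62 rows take the 38% as the only other loss. The fall is 0.3 to 0.5 points at 1% and 1.7 to 2.4 points at 5%. These figures apply to two doses against two doses. Where the reference is one dose of 5×10^10 vp, its Day 29 sample is kept, so the fall would be smaller.

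**The case against.** **Timing.** Amendment 7 describes main-study and sub-study recruitment in the past tense, some participants had already passed their 6-month visit, and the SAP reports blinded Day 71 N-serology. Few participants may still have had dose 2 pending. This stands, and it is the main limit on the benefit. The documents do not give the number.

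**The hazard was already handled.** Participants are discouraged from outside serology, and Section 7.1 speaks of a positive test for infection and offers sponsor contact. This lowers the frequency and gives a site a reason to ask. It is still not an exception: Section 7.1 refers back to 8.3.1, where serology counts, and case-by-case queries may be answered differently across sites.

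**Precaution.** A dosing rule may be stricter than an analysis rule, and a spike-only positive does not exclude infection. A reader might infer that the protocol and SAP contradict each other. They do not, because one governs dosing and the other sample exclusion. The precaution is nevertheless weak here: the sub study plans both doses for baseline-seropositive participants, and 8.3.1 already drops serology as a trigger for them.

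**Stronger readings.** A reader might infer that higher dose levels produce more spike positives and hence selective loss of Day 71 data. The documents contain no data on off-study testing by dose, so no bias is shown. Nor does the rule make the analysis count false positives as infections, since the SAP's definition excludes spike serology. Reporting the result as an adverse event is not at fault either, because Section 10.4.1 includes abnormal diagnostic results in the AE definition.

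**Conclusion.** The point holds as a narrow fault in a dosing rule. For baseline-seronegative participants, dose 2 is withheld on a test result that the protocol says the vaccine can produce, with no written way out. The consequence is a lost dose and a lost Day 71 sample for an uninfected responder; Day 29 is unaffected.

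The size cannot be established from the documents. The 1% to 5% range is an assumption, and the true figure is probably low, because it needs an off-study spike test, positive, taken before dose 2 and reported, in someone asked not to test. Even at 5% the power effect is modest, so a claim that the rule materially underpowers the study is not supported. The case rests on the mismatch between rule and warning and on an avoidable missed dose. Priority: minor, cheap improvement, of use only to participants who have not yet received dose 2.

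**What to change.** In Section 8.3.1, footnote r (1.4.1 and 1.4.2), and Sections 4.1, 8 and 10.4.1:

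- For baseline-seronegative participants, limit the off-study serology trigger for withholding dose 2 to non-spike assays (for example N), in line with the SAP's infection definition.
- Leave PCR/molecular positives as a bar.
- If the assay target is unknown, resolve it by a site query or by N-serology on study serum, a use that footnote l already permits. If this cannot be done within the dosing window (−3/+7 days around Day 57), the current rule stands.
- Record the assay target (spike, non-spike, unknown) with each off-study serology result.

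Infection coding in the analysis needs no change.

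The cost is aligned wording, some site queries and one eCRF field, unless the eCRF, which is not among the documents, already captures the target. The downside is an occasional dose given to a participant with an undetected infection. Central N-serology turnaround is not stated, and after Day 29 the next scheduled draw is the Day 57 pre-vaccination sample, so some late unknown-target cases would still miss dose 2.
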